8.2. Evaluations During Study

8.2.1. Before each drug administration

Every patient needs to be evaluated by the treating physician before each drug administration with the following laboratory tests. Overlapping baseline tests can be combined with tests required for cycle 1 of drug administration as long as these baseline tests occur within 3 days before cycle 1:

- CBC with differential/platelets
- Serum chemistry studies to include sodium, potassium, chloride, carbon dioxide, BUN, creatinine, glucose, magnesium, calcium, phosphorus, albumin, total protein, SGOT (AST) or SGPT (AGT), total bilirubin, alkaline phosphatase and uric acid.
- TSH measurement
- Patient weight for dose calculation purposes

8.2.2 DLT assessment (Concurrent- group 1 & 3: Cycle 2, Day 1/Day 8 (Day 29); Sequential-group 2: Cycle 3, Day1 (Day 43).

- Physical examination to include weight and vital signs.
- Physical examination, interim history pertaining to any change from baseline, current medications and treatment-related toxicities. Adverse events will be monitored using the NCI CTCAE Version 4.0.
- Laboratory testing CBC with differential/platelets
- Serum chemistry studies to include sodium, potassium, chloride, carbon dioxide, BUN, creatinine, glucose, magnesium, calcium, phosphorus, albumin, total protein, SGOT (AST) or SGPT (AGT), total bilirubin, alkaline phosphatase and uric acid.

8.2.3. Follow up - every 2 to 4 months

- Physical examination to include weight and vital signs.
- Physical examination, interim history pertaining to any change from baseline, current medications and treatment-related toxicities. Adverse events will be monitored using the NCI CTCAE Version 4.0.
- Laboratory testing CBC with differential/platelets
- Serum chemistry studies to include sodium, potassium, chloride, carbon dioxide, BUN, creatinine, glucose, magnesium, calcium, phosphorus, albumin, total protein, SGOT (AST) or SGPT (AGT), total bilirubin, alkaline phosphatase and uric acid.
- All appointments after the last cycle of BMS-986156 will allow a window of ± 1 months.
- Radiation oncology follow up appointments will be at the discretion of the treating radiation oncologist. We recommend follow up at 3 and 6 months after the completion of the last cycle of BMS-986156 followed by appointments as per standard of care.

8.2.4. Re-induction follow up

Follow up with radiation oncology will be scheduled at the end of every 3rd study cycle and every 2-4 months from completion of last cycle of drug .

- Imaging studies: Response assessment during and post treatment should be performed using the same modality as the pretreatment assessment whenever feasible, and all lesions assessed pretreatment must be included in the post-treatment evaluation:
 - CT scans of the chest, abdomen and/or pelvis (preferred); or
 - MRI of abdomen and pelvis; or
 - PET/CT (preferred)

- All appointments after the last cycle of BMS-986156 will allow a window of ± 1 months.

8.2.5. Tumor biopsies and serum biomarker evaluation

All patients with accessible tumor will undergo a baseline biopsy of a non-irradiated tumor and a post SBRT biopsy of an irradiated tumor, with low dose radiation, or non-irradiated tumor, as well as a biopsy at the point of progression as determined by the treating physician or PIs of the study. Blood will be drawn with baseline labs, during week 1 of cycle 2 (group 1) or on the last day of radiation treatment (groups 2 and 3), and at progression of disease decided by the discretion of the treating physician and/or study PIs. Blood and tissue biopsies will be mandatory. A tentative calendar is shown in Section 12 in Study Calendar group 1, group 2, group 3.

8.3. Measurement of Effect

1. Response and progression will be evaluated in this study using guidelines proposed by the Immune Related Response Criteria (irRC).
2. The best achieved objective response per irRC criteria (as described below) will consider all imaging conducted after week 1 of cycle 5 for group 1 and 2, or week 2 cycle 3 for group 3 of drug administration. After initial response imaging is obtained, additional imaging will be obtained every 12 weeks (± 4 weeks, or sooner if clinically indicated by treating physician's or PIs discretion) for re-evaluation of treatment response. If in the event that patient receives re-induction, imaging will be obtained after the 4th cycle of re-induction and every 2-3 months thereafter. All imaging obtained during and after re-induction will be considered when obtaining the best achieved objective response for patients who got re-induction treatments.

irRC: Measurable Disease Prior to Therapy (day <1)

Index lesions: Up to 15 index lesions per patient (5 per organ, up to 10 visceral and 5 cutaneous) with minimum size 5 x 5 mm will be accurately measured in two dimensions (two largest perpendicular diameters) on CT or MRI scan (slice thickness no greater than 5 mm) prior to therapy initiation. Lesions measured with calipers by clinical exam may be conducted on lesions no smaller than 10 mm in the smallest dimension. Lesions that cannot be accurately measured with calipers should be recorded as non-measurable.

SBRT-treated index lesions: Defined as all index liver and lung lesions treated by SBRT as part of this protocol.

Non-SBRT-treated index lesions: Defined as all index lesions not treated by SBRT as part of this protocol.

irRC: Index and non-Index Lesions:

For the irRC, index and measurable new lesions are taken into account (in contrast to conventional WHO treatment response criteria, which do not require the measurement of new lesions, nor are new lesion measurements included in the assessment of evolving tumor burden). At the baseline tumor assessment, the sum of the products of the two largest perpendicular diameters (SPD) of all index lesions (five lesions per organ, up to 10 visceral lesions and five cutaneous index lesions) is calculated. At each subsequent tumor assessment, the SPD of the index lesions and of new, measurable lesions ($\geq 5 \times 5$ mm; up to 5 new lesions per organ: 5 new cutaneous lesions and 10 new visceral lesions) are added together to provide the total tumor burden. In addition to a global irRC

which will encompass all lesions under the previous definition, the irRC of lesions included within the SBRT PTV and outside the SBRT PTV will also be assessed as follows:

1. **Global irRC:** irRC that factors all lesions including both index and non-index as outlined in 9.5.
2. **In-Field irRC:** irRC in which only index within the SBRT PTV will be considered and any non-index lesions arising inside the SBRT PTV
3. **Out-Field irRC:** irRC in which only index lesions outside the SBRT PTV will be considered and any non-index lesions arising outside the SBRT PTV

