All patients who achieve systemic benefit (based on physician discretion) but later progress will be given the option of receiving reinduction. Optional radiation can be administered during reinduction. If administered, radiation will be given similar to what was done in the initial treatment. After the first round of reinduction, patients may receive additional reinduction if during their most recent post cycle 4 imaging disease control is observed without severe (grade >3) toxicity. Patients with either liver or lung lesions amenable to SBRT (either 50 Gy in 4 fractions or 60 Gy in 10 fraction) will be enrolled on this trial.

Treatment group 1) Ipilimumab + BMS-986156 (30 mg / 100 mg) x 4 for safety assessment (No SBRT) → Nivolumab x 26

Treatment group 2) Sequential (late SBRT) Ipilimumab + BMS-986156 (dose as determined in group 1) x 2 → SBRT → Ipilimumab + BMS-986156 (dose as determined in group 1) x 2 → Nivolumab x 26

Treatment group 3) Concurrent (early SBRT) Nivolumab (480 mg Q4W) + BMS-986156 (30mg) + SBRT → Nivolumab + BMS-986156 x 3 (30mg) → Nivolumab x 22

Group 1, 20 patients: Ipilimumab + BMS-986156 (30 or 100 mg) Dose Escalation → Nivolumab x 26 (up to 2 year maintenance)

Day 1 and every 21 days: Ipilimumab therapy at 3 mg/kg as a 90 minute intravenous (IV) dose and BMS-986156 at either 30 mg or 100 mg dose as a 60 min IV dose will be given in an outpatient setting. Dose cycles will be repeated every 21 days: on days 1, 22, 43, and 64 for a total of 4 cycles. Maintenance therapy of Nivolumab (480mg Q4W) will start day 85 and continue every 28 days, for 26 cycles.

A modified 3+3 dose escalation then expansion to a total of 10 patients per arm (escalation + expansion, if applicable) will be performed on two dose levels of this combination therapy. Details on de-escalation are presented under section 7.7.1.

Group 1

[figure not shown]

Diagram of Treatment Schedule for Ipilimumab + BMS-986156 (30 or 100 mg) Dose Escalation → Nivolumab x 26 (Treatment Group 1)

Group 2, 20 patients: Ipilimumab + BMS-986156 x 2 → SBRT → Ipilimumab + BMS-986156 x 2 → Nivolumab x 26 (up to 2 year maintenance)

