Day 1 and every 21 days: Ipilimumab therapy at 3 mg/kg as a 90 minute intravenous (IV) dose and BMS-986156 (dose as determined in group 1) as a 60 min IV will be given in an outpatient setting. Dose cycles will be repeated every 21 days: on days 1, 22, 43, and 64 for a total of 4 cycles. Nivolumab (480 mg Q4W) will start day 85 and continue every 28 days for 26 cycles. Enrollment of this group will start based on the following criteria. If 2 out of 6 patients, or less, display DLTs, then, enrollment of group 2 can begin. Alternatively, if 3 out of 6 patients, or more, display DLTs, then, enrollment of group 2 cannot begin until 10 patients have been treated in group 1.

SBRT: SBRT will be given after 2 doses of ipilimumab and BMS-986156 on days 29-32 for 50 Gy in 4 fractions or on days 29-40 for 60 Gy in 10 fractions (no SBRT during weekends): SBRT will be directed at 1-4 targetable liver or lung lesion(s). To minimize treatment breaks, patients may start radiation on a Monday.

Group 2

[figure not shown]

Diagram of Treatment Schedule for Ipilimumab + BMS-986156 x 2 → SBRT → Ipilimumab + BMS-986156 x 2 → Nivolumab x 26 (Treatment group 2).

Group 3, 20 patients: Nivolumab + BMS-986156 x 1 + SBRT → Nivolumab + BMS-986156 x 3 → Nivolumab x 22

First dose of Nivolumab + BMS-986156 and SBRT will be given concurrently (early) and followed by Nivolumab + BMS-986156 x 3; then, Nivolumab monotherapy for 22 cycles. Nivolumab will be administered for a total of 26 cycles, either as a combination or monotherapy, in this group. Enrollment of patients for this group will start around the same time as group 1. Choice of treatment group will be at the discretion of PI and treating physician.

Nivolumab therapy at 480 mg dose will be given on day 1 as a 30 minute IV dose and BMS-986156 at 30 mg dose will be given on day 1, 29, 57, 85 as a 60 min IV in an outpatient setting. Nivolumab monotherapy will start on day 113 and will continue for 22 cycles.

SBRT: SBRT will be given on days 1-4 (days 2-5 are acceptable if scheduling does not permit radiation to begin same day as infusions) for 50 Gy in 4 fractions or on days 1-12 for 60 Gy in 10 fractions (no SBRT during weekends). SBRT will be directed at 1-4 targetable liver or lung lesion(s). To minimize treatment breaks, patients may start radiation on a Monday.

Group 3

[figure not shown]

Diagram of Treatment Schedule for Nivolumab + BMS-986156 x 1 + SBRT → Nivolumab + BMS-986156 x 3 → Nivolumab x 22 (Treatment group 3)

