2.2. Secondary Objectives

- To determine antitumor activity of ipilimumab therapy with BMS-986156 (30 or 100mg) as well as Nivolumab with BMS-986156 (30 mg) with SBRT treatment for 1-4 lung lesions in both the SBRT treated lesion and non-irradiate tumors.

- b) To determine antitumor activity of ipilimumab therapy with or without BMS-986156 (30 or 100mg) as well as Nivolumab with BMS-986156 (30 mg) with SBRT treatment for 1-4 liver lesions in both the SBRT treated lesion and non-irradiate tumors.
- c) To compare response and progression of the non-irradiated tumors between BMS-986156 with ipilimumab vs BMS-986156 with Nivolumab, using irRC.
- d) To evaluate the predictive potential value of tumor-associated and systemic immune biomarkers for therapy effectiveness and toxicity prediction.
- e) To evaluate whether skeletal mass, neutrophil, neutrophil to lymphocyte ratio, and tumor bulk are correlated with clinical outcomes and adverse events.
- f) To evaluate whether tumor kinetics in combination with clinical correlates can help determine treatment response. The radiological response and clinical data will be analyzed using mathematical and statistical models to identify prognostic groups.
- g) To evaluate whether tumor mutational burden correlates with improved clinical outcomes and response criteria.

3. Background

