- For nivolumab/BMS-986156: Extensions to the period of dose delays may be granted for individual subjects on a case by case basis decided by the Investigator in settings where benefit/risk may justify continued study therapy (e.g., subject deriving clinical benefit who requires prolonged steroid taper for management of non-DLT drug-related AEs, or experiences delays for management of a non-drug related AE).
- The end of cycle tumor assessments (i.e., CT/MRI, positron emission tomography, etc) will continue on an every 8 weeks schedule relative to the subject's 1st dose regardless of any treatment delay incurred.

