10.2.4. Efficacy Analyses

Treatment success and clinical benefit will be defined as irCR or irPR or irSD, assessed using irRC (e.g. the best response obtained by a patient). Clinical benefit will be established as having irCR or irPR or irSD > 6 months. Measurements from all imaging, including those obtained during and after re-induction, will be considered in this analysis. Patients will be continuously evaluated for disease response via imaging until they are removed from the study. For secondary objectives a), b), and c), success probabilities will be estimated for each target separately (liver, lung) along with appropriate 95% confidence intervals. Safety comparisons among the groups will be assessed (primary end points) and efficacy comparisons between groups will be assessed with regard to the irRC outcomes while global, in-field irRC will be used for

hypothesis generating using Pearson chi-squared or Fisher exact tests. For secondary objective d) comparisons will be performed between group 2 and 3 as well as per treatment site (liver, or lung).

1. **Global irRC:** irRC that factors all lesions both index and non-index as outlined in 8.3.
2. **In-Field irRC:** irRC in which only SBRT-treated lesions will be considered and non-index lesions arising inside the SBRT PTV
3. **Out-Field irRC:** irRC in which only non SBRT-treated lesions will be considered and non-index lesions arising outside the SBRT PTV

For the secondary objective comparing the response between the arms. With 20 patients per arm, we would have 80% power using a two-sided 10% alpha with a chi-squared test to detect the following differences in response rates between treatment groups 44% vs 10%, 57% vs 20%, 68% vs 30% and 78% vs 40%. To increase statistical power, we may also combine the patients into a single dataset and fit a logistic regression model with response (CR+PR) as the outcome and SBRT dose, target (liver or lung) among other factors (including but not limited to: number of metastatic disease sites, number of prior treatments, primary cancer histology, age, pre-treatment KPS and Royal Marsden Score) as the predictors.

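### Under section 8.3, response in groups 1 and 2 is read only after nivolumab has started, so it cannot be attributed to ipilimumab/BMS-986156, and objective c) compares two sequences that both contain nivolumab

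*Combined protocol and SAP*

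**What the plan says.** Secondary objectives a) and b) (section 2.2) ask for the antitumor activity of ipilimumab with BMS-986156 and of nivolumab with BMS-986156. Objective c) compares response and progression of non-irradiated tumors "between BMS-986156 with ipilimumab vs BMS-986156 with Nivolumab, using irRC".

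Section 1 gives ipilimumab/BMS-986156 in groups 1 and 2 "on days 1, 22, 43, and 64 for a total of 4 cycles". For group 1 it continues: "Maintenance therapy of Nivolumab (480mg Q4W) will start day 85 and continue every 28 days, for 26 cycles". For group 2: "Nivolumab (480 mg Q4W) will start day 85 and continue every 28 days for 26 cycles". In group 3, "BMS-986156 at 30 mg dose will be given on day 1, 29, 57, 85 as a 60 min IV", with nivolumab given from day 1.

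Section 8.3 states that best response "will consider all imaging conducted after week 1 of cycle 5 for group 1 and 2, or week 2 cycle 3 for group 3", and section 10.1.2 sends the reader to 8.3 for tumor response. Other sections do not fit this:

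- **Counted scans.** Section 10.2.4 admits measurements from all scans, including those during and after re-induction, and gives no start point.
- **Scan interval.** Section 7.3.3 says tumor assessments "will continue on an every 8 weeks schedule relative to the subject's 1st dose". Section 8.3 and the notes to the group 1 and group 3 calendars say every 12 weeks, with 4 weeks' allowance either way.
- **irSD.** Section 10.2.4 first says "Treatment success and clinical benefit will be defined as irCR or irPR or irSD, assessed using irRC", with no minimum duration. Its next sentence requires more than 6 months. Section 8.5.1 has a third wording, irSD for up to 6 months.

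**The concern.** The objectives name a drug pair, but under 8.3 the response in groups 1 and 2 is read only once a different drug has been added. Section 5.3.5 reports durable responses to nivolumab monotherapy in several tumor types, so maintenance could itself produce responses. Under the present rule, such a response in group 1 or 2 is credited to ipilimumab/BMS-986156.

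The benchmark is low. Section 3.3 cites 10% out-of-field irPR for ipilimumab with SBRT, and each group has 20 patients, so one converted patient moves the rate by 5 points (1/20). In objective c) both sides would be read on nivolumab. The result would describe two sequences, not ipilimumab against nivolumab as partners for BMS-986156. Because the sections also disagree on which scans count, two analysts could report different response rates from the same data.

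**Working it through.** **Plan's own figure.** Section 10.2.4 claims 80% power with 20 per arm, two-sided 10% alpha and a chi-squared test. With pooled variance and no continuity correction, power = Φ{[|p1 − p2| − 1.645·√(2p̄(1 − p̄)/20)] / √[(p1(1 − p1) + p2(1 − p2))/20]}. For 44% v 10%, p̄ = 0.27 and power = Φ[(0.34 − 0.231)/0.130] = 0.800. The other three pairs give 0.794, 0.794 and 0.807. The stated figure is reproduced, so the issue is what the response rates measure.

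**Day count, groups 1 and 2** (21-day cycles, section 1):
- Cycle 5 day 1 = 1 + 4 × 21 = day 85, the first nivolumab dose.
- Week 1 of cycle 5 = days 85 to 91, so counting starts on day 92, 7 days after that dose.
- irCR and irPR need confirmation at least 4 weeks later (section 8.5.1): 92 + 28 = day 120, after nivolumab on days 85 and 113.
- Best response then runs through up to 26 × 28 = 728 days of nivolumab cycles.

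If the cut-off is read as from week 1, a scan on day 85 before the infusion could count. Nothing requires that order, and confirmation would fall on day 85 + 28 = 113 or later, still on nivolumab. The 8-weekly scan in 7.3.3 would fall at about day 57, before any nivolumab, but 8.3 does not count it.

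**Day count, group 3** (28-day cycles):
- Cycle 3 day 1 = 1 + 2 × 28 = day 57; week 2 = days 64 to 70; counting starts on day 71.

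**Gap between groups:**
- From day 1: 92 − 71 = 21 days later in groups 1 and 2.
- From SBRT start (day 29 in group 2, day 1 in group 3): 92 − 29 = 63 days v 71 − 1 = 70 days, so group 2 is read 7 days earlier.

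**Illustration of the attribution problem.** The conversion rates are assumed; the documents give none. Take true rates of 10% (ipilimumab side) and 44% (nivolumab side), the plan's first pair. Let nivolumab convert a share c of ipilimumab-side non-responders before best response is read. Observed rate = 0.10 + 0.90c.

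| c | observed ipilimumab-side rate | power v 44% |
|---|---|---|
| 0 | 10% | 0.80 |
| 5% | 14.5% | 0.67 |
| 10% | 19% | 0.52 |
| 20% | 28% | 0.275 |

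If the ipilimumab side were truly the better one, conversion would widen the observed difference instead. The direction of the distortion is therefore not known in advance.

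**Limits.** The column headers of the group 1 and group 2 calendars did not survive in the text, so their scan columns were not used. The group 3 calendar, as extracted, seems to place the first scan in week 1 of cycle 3 (days 57 to 63), before the 8.3 cut-off. Check this in the original table.

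**The case against.** Several points on the other side stand.

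- Section 10.2.4 sets no start point, so the statement that all counted scans follow nivolumab is true of 8.3 but not of every section. This is a conflict to report. It does not rescue the plan, because 10.2.4 defines no read before nivolumab either.
- Late reading has a rationale. Section 3.1.1 says ipilimumab's effect may take weeks to months and cites first responses from day 40 to day 441.
- Nivolumab maintenance is a planned part of groups 1 and 2, so a comparison of whole sequences is legitimate and can be made descriptively. A scan 7 days after one nivolumab dose still largely reflects the first 12 weeks.
- Section 10.2.1 labels the comparisons exploratory, groups are assigned at the discretion of the investigator and treating physician, and the primary objectives are safety. No scan rule would make the contrast clean.

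A reader might also infer that group 3's earlier first scan inflates its success rate through irSD. With exponential time to progression and medians of 60 to 120 days, the difference in patients still progression-free between days 64 and 85 is 8 to 10 points. The documents do not support that figure:

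- They give no such medians.
- irPD needs confirmation at least 4 weeks later.
- 10.2.4 also has an irSD definition of more than 6 months, and its logistic model defines response as CR plus PR, without irSD.
- The 21-day gap becomes 7 days in the other direction when counted from SBRT start.

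**Conclusion.** The point holds as one of attribution and labelling. Under 8.3, the first counted scan in groups 1 and 2 is at about day 92, confirmation is at about day 120 or later, and up to 26 nivolumab cycles lie inside the best-response window. Response there cannot be assigned to ipilimumab/BMS-986156. Objective c), as analysed, compares sequences that both contain nivolumab and, for group 2 v group 3, also differ in SBRT timing.

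A reader might go further and conclude that the activity of these regimens cannot be measured at all. That does not follow: the full sequences remain measurable, and only the contribution of the ipilimumab/BMS-986156 phase is lost. The size of any distortion is unknown; the power table rests on assumed conversion rates. The unequal start of counting is a minor matter.

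This should be fixed. It concerns exploratory secondary comparisons in non-randomised groups and does not affect the primary safety objectives.

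**What to change.** 1. In groups 1 and 2, schedule the existing first response scan before the actual first nivolumab dose, and count it. Tie it to the dose and not to a fixed day, because the calendar notes allow day 85 plus or minus 3 days.
2. Read group 3 at a matching time from day 1, about week 12 (days 78 to 84, week 4 of its cycle 3). Report time from SBRT start as well: at days 78 to 84, group 2 is 49 to 55 days from SBRT start and group 3 is 77 to 83, a 28-day difference. No single day aligns both clocks.
3. For objectives a) to c), report response status at that scan as the induction-phase result, and flag that in groups 1 and 2 the confirmation scan is on nivolumab.
4. Keep best response over all scans as a second result, labelled as the full treatment sequence, and word objective c) to match.
5. Reconcile 7.3.3, 8.3, 10.2.4 and the calendars on scan interval and counted scans. Settle one irSD definition across 8.5.1 and 10.2.4.

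**Cost.** Wording changes and a shifted scan, with no extra scan and no change to treatment. In groups 1 and 2 the scan moves 8 to 14 days earlier than day 92. In group 3 it moves 7 to 13 days later than day 71, or up to 27 days later (day 57 to day 84) if the calendar does place it in week 1 of cycle 3. A week-12 read misses late immune responses, which is why the all-scan result must stay. A pre-nivolumab scan that was not taken cannot be recovered afterwards.
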